14.8 Deaths

All deaths, regardless of cause, that, occur between the time a subject signs an informed consent document and the final study visit or 30 days after the last dose of study product, whichever is longer, must be reported to Primus by telephone with a follow-up fax within 24 hours of the investigator becoming aware of the death. This applies whether or not the

subject has received study product and whether or not the study product is thought to be causally related to the death. It is the investigator's responsibility to obtain all relevant medical records and autopsy reports and forward them to Primus as soon as possible.

14.9 Reporting Safety Information to IRB

It is the responsibility of the investigator to notify his/her IRB of any unexpected or unknown risk to study subjects. This includes death from any cause and all SAEs. The investigator should make this report within 14 days of the onset of the SAE. The report should include any action taken after discussion of the SAE with Primus.

14.10 Managing Adverse Events

All AEs and SAEs should be medically managed according to the best medical standards available in the investigator's community. Except in the case of emergent treatment and routine care, the management of the event should be discussed with Primus. Decisions regarding re-challenge with study drug **must** be made in consultation with Primus.

14.11 Pregnancy

EpiCeram is device whose ingredients include at least 2 occlusive products (petrolatum, dimethicone) that prevent systemic uptake and therefore the device has no impact on the reproductive system of the user. Pregnancy data will not be collected during this study.

DEFINITION OF DEVICE PER FDA: Per Section 201(h) of the Food, Drug, and Cosmetic Act, a device is: An instrument, apparatus, implement, machine, contrivance, implant, in vitro reagent, or other similar or related article, including a component part, or accessory which is:

...3. intended to affect the structure or any function of the body of man or other animals, and which does not achieve its primary intended purposes through chemical action within or on the body of man or other animals and

which does not achieve its primary intended purposes through chemical action within or on the body of man or other animals and which is not dependent upon being metabolized for the achievement of its primary intended purposes. The term "device" does not include software functions excluded pursuant to section 520(o).

15.0 Ethical Considerations

This study will be conducted in accordance with the principles of the Declaration of Helsinki, ICH guidelines and Good Clinical Practices (GCPs) and US FDA regulations.

15.1 Informed Consent

All patients must read and sign the institutional review board (IRB) approved Research Subject Information and Consent Form before they can be subjects in this research study. It is the investigator's responsibility to fully inform the patient about the procedures, risks and benefits of the study and to answer, in a manner clearly understandable to the patient. The consent must be obtained and documented according to the instructions of the IRB. A copy of the signed and dated document must be given to the subject. The IRB approved document must not be modified in any way from its original form. The original copy must be retained with the subject's study file and is subject to inspection by representatives of Primus and regulatory agencies.

All written material read by or distributed to a subject during the study must be written in a language the subject can read and understand and approved by the IRB.

15.2 Institutional Review Board (IRB)

For all studies performed in the United States, Primus will assume responsibility for submitting the required documents to a central IRB. Before this can be done each investigator must submit the following to Primus:

- a. Signed and dated protocol signature page.
- b. Completed, signed and dated FDA Form 1572, when required.
- c. Completed, signed and dated W-9 form.
- d. Current curriculum vitae for investigator and all sub-investigators, signed and dated.
- e. Investigator conflict of interest form.

If an investigator wishes to use an IRB other than that selected by Primus, he/she may do so after obtaining approval from Primus. In this case, the investigator will be responsible for all required submissions. Non-U.S.A. investigative sites will have IRB approval arranged by the contract research organization (CRO) engaged by Primus for the execution of the study. Any changes to the model consent must be first approved by Primus, in writing. The investigator must agree to all protocol amendments and, if necessary, make appropriate changes in the consent. The IRB should be notified of any such changes and IRB approval must be sought for any changes involving subject safety.

Serious or unexpected adverse events must be reported to the IRB according to their instructions.

All investigators will be responsible for completing reports as required by the IRB. One copy of those reports should be kept in the study regulatory file and another submitted to Primus.

15.3 Subject Confidentiality

Subject identities should always be protected. This is the legal responsibility of the investigator. Subjects should be identified in study documents only by initials and study number on any document sent to Primus or a regulatory agency. Documents that are only for office use must be kept in strict confidence. It is strongly recommended that the investigative site have its own HIPAA document in place and that patients read, sign and date this at the same time they sign the consent.

Investigators must allow representatives of Primus or government regulatory agencies to inspect study records with subject de-identification in place.

16.0 Administrative and legal obligations

16.1 **Pre-study Documentation**

Before an investigator can begin screening subjects and before shipment of study product can commence the investigator must complete and return the following to Primus:

- a. Signed and dated protocol signature page
- b. Completed, signed and dated FDA Form 1572, when required
- c. Copy of IRB approved consent
- d. Copy of IRB approval letter
- e. Current CVs of the investigator and all sub-investigators, signed and dated
- f. Name, address and telephone number of any local laboratories to be used in the study
- g. Normal values for local laboratory
- h. Agreement to dispose of unused drug supplies per their community requirements
- i. Signed and dated contract to conduct the study under the conditions and financial arrangements specified
- j. Financial disclosure form
- k. Name and contact information of person(s) responsible for the day to day management of the study

16.3 Protocol Amendments

Protocol amendments may be made only by Primus. The investigator's IRB must be informed of any amendments that may affect subject safety or the conduct of the study. The IRB must issue a letter of approval of such amendments. The investigator must keep the original letter in the study's regulatory binder and forward a copy of the letter to Primus.

16.4 Study Termination

Both the investigator and Primus have the right to terminate their participation in the study. If this is done by the investigator, he/she must provide a detailed explanation of the action to Primus and the IRB and a copy of this account must be retained with the regulatory file.

Upon completion of the study the investigator is required to send a summary of his/her experience to Primus and to the IRB. This should include an impression of clinical response and an accounting of any AEs or SAEs thought to be possibly associated with the study product.

16.5 Source Documents

FDA regulations (21 CFR 312.62b) require an investigator "to prepare and maintain adequate and accurate case histories that record all the data and other observations pertinent to the investigation on each individual" participating in a clinical investigation whether or not they were administered the investigational product. "Case histories include the case report forms and supporting data including, for example, progress note of the physician, the individual's hospital charts, and nurses' notes. The case history for each individual shall document that informed consent was obtained prior to participation in the study." Source documents may be reviewed and compared with data collection tool/CRFs at all monitoring visits. All source documents and data collection tool/CRFs should be complete and up to date and filed in chronological order in the subject's study file.

The investigative site must maintain logs for the following:

- a. Screening visits
- b. Randomization
- c. Study product dispensed and returned
- d. Monitor visits
- e. Study personnel
- f. Telephone contact

16.6 Data Collection Tools/Case Report Forms

Primus will provide investigators with data collection tool (hard copy or electronic) bearing information identifying the study site and the principal investigator. All data obtained during the study will be recorded on the data collection tool. This data will be reviewed on site or electronically by a Primus clinical monitor (or an agent of Primus such as a contract research organization) who will forward one copy to Primus (if hard copy), the original to remain with the subject's study data file.

The data collection tool contains the critical study data and are the basis from which results are tabulated, analyses performed, and final reports made. Therefore, it is essential that data recorded be legible, complete and accurate. Forms should be typed or completed in black ball point ink (if hard copy). Corrections should be made by placing a single line through the error, adding the correct data then signing and dating the correction. Under no circumstances should the original entry be erased, overwritten, or obscured by white-out or some other method. The data collection tool should contain only de-identified information. All data points must be answered. If the information is unknown or unavailable the terms "NA" (not available), "ND" (not done), "SU" (subject unable) or "DP" (data pending) may be used.

The investigator must maintain all records in a complete and current state. All source documents and supporting materials must be available for inspection by Primus personnel or representatives of government agencies.

16.7 Final Study Documentation and Storage

Investigators must retain all study records in a secure location, safe from environmental damage, for the maximum time required by the FDA, Primus or his/her institution, whichever is longest. These records should include, but are not limited to, the following:

- Source documentation
- Data collection tool/CRFs

- Original reports of tests results
- Protocols with amendments
- Original signed and dated ICF(s)
- Product accountability and dispensing logs
- Correspondence with Primus, IRB and governmental agencies

The investigator must complete a summary report (form provided) and submit it to Primus upon completion of the study. All data and other information may be submitted to the governmental regulatory agencies as required by the regulations. No study document may be destroyed without the written permission of Primus. Any change in storage location or assignation of the records to another party must first be approved, in writing, by Primus. If, for any reason, the investigator becomes unable to store study documents Primus must be notified. Study documents should never be destroyed without the written consent of Primus.

17.0 Summary of Investigator responsibilities

Investigator responsibilities include, but are not limited to:

- a. Will conduct the study according to the protocol and will make no changes without the consent of the sponsor. This requirement is not intended to limit the investigator's ability to deviate from the protocol to protect the health and welfare of a subject.
- b. Will comply with all applicable regulatory requirements.
- c. Will personally supervise the conduct of the study.
- d. Will report any adverse events that occur during the study.
- e. Will promptly treat or arrange for treatment of any AE or SAE.
- f. Has read and understands the information contained in the investigator's Brochure or product information document.
- g. Will attend any investigator meetings conducted by Primus.

17.1 Data Collection and Study Monitoring

This study will be monitored, in person or electronically, by Primus personnel or by clinical research associates (CRAs) employed by Primus for this project. Site visits, if necessary, will be scheduled at pre-established intervals and will be scheduled in advance. All site visits will be conducted according to Primus' standard operating procedures (SOPs). The monitor must be allowed free access to all study records and supporting in order to verify the accuracy, consistency and completeness to ensure the study is being conducted in accordance guidelines of good clinical practice. Some site visits may be conducted remotely using an internet, based system with which the monitor and coordinator can view and speak to each other and work simultaneously on documents in real time. Study coordinators must be available and be able to devote the required time to the site visit. The primary investigator or sub-investigator should also be available to offer comments and resolve any issues that may arise.

18.0 Audits

The investigative site may be subject to audit by Primus or by regulatory agencies. All areas of the site will be examined including, but not limited to, subject treatment rooms, laboratory, product storage and preparation areas, and document storage. To prepare for any audit all data and documentation must be complete and organized chronologically by document type. If a site is notified of impending regulatory agency audit the primary investigator should promptly inform Primus to arrange for audit preparation assistance.

20.0 Publication/presentation of data

Primus regards all information obtained from the conduct of this study as confidential. If an investigator wishes to publish or present in oral or written form all or part of the data obtained during the study he/she must first submit a complete copy of such presentation to the director of Clinical Investigation for review and approval. This submission must occur no later than sixty (60) days before the anticipated date of presentation. The investigator will be required to incorporate any suggestions made by Primus consistent with its right to protect the confidentiality of the information.

21.0 Statistical considerations

Descriptive statistics will be calculated for all demographic and clinical characteristics at baseline and study outcomes for each time period. Means and standard deviations will be

presented for continuous variables (e.g. age) or proportions and frequencies for categorical variables (e.g., sex) to describe the sample.

Paired t-tests will be used to assess differences in the primary outcomes of face and hand skin irritation symptoms (pain, redness, dryness, cracking, roughness, itching and overall skin irritation) between the baseline visit and Day 28 follow-up visit. The same analysis will be conducted for the secondary outcomes of pH, TEWL, and S. aureus colonization level. All statistical tests for the primary outcomes will be conducted will be two-tailed with α set at 0.05. All *p*-values will be reported with high precision (to the 4th decimal place) so that multiple comparisons adjustments may be applied, as desired. Table 1 below shows how the results will be presented.

The analysis will be performed on the Intention-to-Treat sample. If there is attrition over the course of the study, attritors will be compared to completers in terms of measures taken at baseline. Any significant differences will be reported.

All variables will be checked for outliers and skewness by visually examining boxplots. Further evaluation of any outliers identified through visual checks will be conducted to assess if any participants should be excluded from the analysis. The assumptions for each inferential statistical test will be evaluated. In the event assumptions are not met, results from a Wilcoxon signed rank test will also be reported.

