- 1. Change in patient reported outcome of face and hand skin symptoms from baseline to Day 28, of at least 2 points on a 0-10 point scale where 0 = none and 10 = worst.
 - a. pain
 - b. redness
 - c. dryness
 - d. cracking
 - e. roughness
 - f. itching
 - g. overall skin irritation

Secondary endpoints

- 1. Change from baseline to Day 28 in pH.
- 2. Change from baseline to Day 28 in TEWL.
- 3. Change in S. aureus colonization from baseline to Day 28.

Inclusion Criteria

- 1. HCW using PPE at least 6 hours/day, 4 days/week or, depending on shift work, 24 hours/week, for at least one (1) month,
- 2. Men or women, any age
- 3. Overall skin irritation score of at least 4 on 0-10 scale where 0 =none and 10 =worst
- 4. Must be willing to stop use of any other emollient and lotion for one (1) week between screening and baseline visit and for the duration of the study.
- 5. Participant is willing to stop use of, or not begin, use of any topical corticosteroids, emollients and lotions to the hands and face for the duration of the trial.

Exclusion Criteria

- 1. History of any skin disorder existing prior to March 1, 2020 characterized by chronic visible lesions or skin irritation symptoms including, but not limited to atopic dermatitis, eczema, moderate-severe acne, chronic dry skin and psoriasis.
- 2. Use of topical or systemic corticosteroids within one (1) month of baseline visit.
- 3. History of any significant medical condition that, in the opinion of the investigator, might put the subject at risk in this trial.
- 4. Participation in another clinical trial within 30 days or 5 half-lives of the study agent, whichever is longer.

Study test item

EpiCeram® 90 gram tubes

Number Subjects

Fifty (50) subjects will be evaluated in this study. Accordingly, 55 subjects will be enrolled to allow for a 10% drop out rate.

Efficacy Measurements

- 1. Symptom scales
 - a. pain
 - b. redness
 - c. dryness
 - d. cracking
 - e. roughness
 - f. itching
 - g. overall skin irritation
- 2. Surface Skin pH
- 3. TEWL
- 4. SCH
- 5. Antimicrobial peptides (LL-37, HBD-2)
- 6. Free fatty acids
- 7. Bacterial qPCR
 - a. S. aureus
 - b. MRSA
 - c. S. epidermidis

Safety Measurements

Adverse Events

Statistics

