Descriptive statistics will be calculated for all demographic and clinical characteristics at baseline and study outcomes for each time period. Means and standard deviations will be presented for continuous variables (e.g., age) and proportions and frequencies for categorical

variables (e.g., sex). Paired t-tests will be used to assess unadjusted differences in primary outcomes of face and hand skin irritation symptoms (pain, redness, dryness, cracking, roughness, itching and overall skin irritation) and secondary outcomes of pH, TEWL, and S. aureus colonization level between the baseline visit and Day 28 follow-up visit. Analysis will be performed on the Intention-to-Treat (ITT) sample. Standard data quality checks will be performed. The sample size of n = 50 is sufficiently powered $(1 - \beta = 0.80)$ to identify a medium effect size of d = 0.4 in a two-tailed test with α set at 0.05. Given the multiple primary endpoints, *p*-values will be reported with high precision (four percentage points) to allow for multiple comparisons adjustments as desired.

EpiCeram for skin protection in healthcare workers using personal protective equipment.

Protocol #: PPE-01

1. Introduction:

During the current COVID-19 pandemic, health care workers (HCW) report that the prolonged use of personal protective equipment (PPE), particularly gloves and face covering, results in irritant contact dermatitis manifested by symptoms of pain, itching, burning and non-specific discomfort of the hands and face and associated visible physical changes of erythema, dryness, roughening and cracking of the affected skin (Jiang, et al 2020). These changes are aggravated by frequent hand washing and antimicrobial alcohol use. These irritative changes are likely associated with defects in the normal barrier structure and function of the skin, including, but not limited to, lowering of pH, excessive water loss, alteration of skin microbiome, lowered resistance to allergens and pathogens and immunological dysfunction. It is unknown whether these changes could increase the likelihood of S. aureus skin contamination or, in people exposed to, but not systemically ill with, COVID-19 to act as "silent" carriers of coronavirus.

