At Visit 3 (Final), 28 days later subjects will complete an overall skin irritation assessment on a 0-10 scale where 0 = none and 10 = worst. Subjects will complete skin symptom scales of pain, redness, dryness, roughness, itching and cracking on a scale on a 0-10 scale where 0 = none and 10 = worst. Photos, skin function and laboratory testing will be in the same location as Visit 2. Photographs: Digital 3D photographs will be taken of the face and back of the hand. The face photo will be a two (2) inch by three (3) inch area of the cheek without identifying features. The hand photo will be the worst area of involvement as selected by the subject.

Skin Function Testing: Measurements of transepidermal water loss (TEWL) with stratum corneum hydration (SCH) and surface skin pH will be taken on the dominant hand on the dorsum of the 3rd and 4th metacarpal phalanges.

Laboratory Testing: Two types of specimens will be obtained; a swab and tape stripping. A single skin swab for bacterial qPCR will be obtained from the palm of the dominant hand. Non-invasive tape stripping of surface cells (3 strips/sample) will be performed at 2 sites; on the web between the 3rd and 4th metacarpophalangeal (MCP) joints on the dorsum of the dominant hand

for antimicrobial peptides (AMP) and three (3) strips/sample from the web between the 2^{nd} and 3^{rd} MCP joints on the dominant hand for free fatty acids. See the manual for detailed instructions on specimen collection. The subject will then be directed to apply EpiCeram to the hands (wrist to fingertips, front and back) and face at least three (3) times daily (about every 8-10 hours), more often if the subject wishes. The investigator will assess the subject' Response to Therapy on a scale of 1-5 with 1 = no response and 5 = best response. Subjects may then be discharged from the study.

4. Primary endpoints

- a. Change in patient reported outcome of overall face and hand skin irritation symptoms from baseline to Day 28, of at least 2 points on a 0-10 point scale where 0 = none and 10 = worst.
- b. Change in any two of the following specific skin irritation symptoms of at least 2 points on a 0-10 point scale where 0 = none and 10 = worst.
 - 1. pain
 - 2. redness
 - 3. dryness
 - 4. cracking
 - 5. roughness
 - 6. itchiness
 - 7. overall skin irritation

5. Secondary endpoints

- a. Reduction from baseline to Day 28 in pH
- b. Reduction from baseline to Day 28 in TEWL

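### The primary endpoint is a change of at least 2 points, defined differently in the synopsis and Section 4, and no described efficacy test uses that threshold

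*Combined protocol and SAP*

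**What the plan says.** **Endpoint.** The synopsis (Primary Endpoint) has one entry, "Change in patient reported outcome of face and hand skin symptoms from baseline to Day 28, of at least 2 points", followed by seven items: six specific symptoms and overall irritation. Section 4 has two entries. Item 4a is "Change in patient reported outcome of overall face and hand skin irritation symptoms from baseline to Day 28, of at least 2 points". Item 4b is "Change in any two of the following specific skin irritation symptoms of at least 2 points on a 0-10 point scale", and its list ends with "7. overall skin irritation", which is already the subject of 4a.

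**Analysis.** The synopsis (Statistics) says "Paired t-tests will be used to assess unadjusted differences in primary outcomes of face and hand skin irritation symptoms", and Section 21 repeats this in nearly the same terms: "Paired t-tests will be used to assess differences in the primary outcomes of face and hand skin irritation symptoms". Section 21 adds a fallback: "In the event assumptions are not met, results from a Wilcoxon signed rank test will also be reported". The synopsis describes the sample of 50 as having 80% power "to identify a medium effect size of d = 0.4 in a two-tailed test" at a significance level of 0.05.

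**Description.** Both places plan means and SDs for continuous variables, and counts and percentages for categorical ones. Section 21 also refers to a Table 1 showing how results will be presented. That table is not in the text available for this review.

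**The concern.** The endpoint carries a size criterion, and the tests do not. A paired t-test or signed rank test asks whether scores moved at all. The endpoint asks whether they moved by 2 points and, in 4b, whether two items did so. The any-two rule reads most naturally as a count within each subject, which a test on the mean of a single scale cannot evaluate.

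The two definitions also differ. Under the synopsis, seven items each carry the threshold. Under Section 4, overall irritation stands alone in 4a and counts again in 4b, so a subject who meets 4a already has one of the two items needed for 4b.

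What is at stake is the meaning of the primary result. An analyst who follows Section 21 exactly obtains primary p-values that do not answer the question posed in Section 4. Two analysts could report the same data as meeting or not meeting the primary endpoint. In an open-label, single-arm study, the 2 points are the only stated size criterion for the primary outcome.

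**Working it through.** **Inputs from the documents:** n = 50 evaluable, d = 0.4, two-sided alpha 0.05, power 0.80 (synopsis, Statistics); threshold 2 points on a 0-10 scale (synopsis and Section 4). The null value of zero is implied by the names of the tests; it is not written out.

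**Assumed:** SD of change 1.5 to 3.0 points. The documents give no SD.

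**1. The plan's own figure.** For a paired t-test the noncentrality is 0.4 × √50 = 2.828 on 49 df.
- Two-sided power is 0.792 (noncentral t), or 0.807 by the normal approximation.
- Required n is ((1.960 + 0.842)/0.4)² = 49.06, so 50 by the normal approximation, or 52 by exact t.

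The stated 80% reproduces, for a mean change against zero.

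**2. Smallest mean change that gives p < 0.05.** This is t(0.975, 49)/√50 = 2.0096/7.0711 = 0.284 SD. The 95% CI half-width for the mean is the same quantity.

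| Assumed SD of change | Mean change at p = 0.05 | Mean change at d = 0.4 |
|---|---|---|
| 1.5 | 0.43 | 0.6 |
| 2.0 | 0.57 | 0.8 |
| 2.5 | 0.71 | 1.0 |
| 3.0 | 0.85 | 1.2 |

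Every entry lies well below 2 points.

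**3. When the powered effect equals the threshold.** 0.4 × SD = 2 requires SD = 2/0.4 = 5.0 points.

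**4. The same check per subject.** Assume normally distributed changes with a true mean of 0.4 SD. The share of subjects with a reduction of at least 2 points is 1 − Φ((2 − 0.4 SD)/SD).
- SD 1.5: 1 − Φ(0.933) = 17.5%.
- SD 3.0: 1 − Φ(0.267) = 39.5%.
- With a cutoff of 1.5, to allow for integer scores, these become 27% and 46%.

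**5. A constructed example.** Of 50 subjects, 25 improve by 1 point, 15 do not change and 10 worsen by 1 point.
- Mean reduction = (25 − 10)/50 = 0.30.
- Variance = (35 − 50 × 0.30²)/49 = 0.622, so SD = 0.789.
- t = 0.30/(0.789/√50) = 2.69 on 49 df, p = 0.0098.
- Wilcoxon signed rank p = 0.011 (exact 0.017).
- Subjects reaching 2 points: 0 of 50.

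The SD here is small. The example shows only that the two questions can have opposite answers; it is not a forecast.

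**The case against.** Several points on the other side have force.

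- **Description is planned.** The planned means would reveal a small average change. The provision for percentages of categorical variables could cover a count of subjects reaching 2 points, and Table 1 might contain such a row. A reader might therefore infer that the plan never reports the threshold at all. The documents do not support that: a descriptive row cannot be excluded. What stands is that no such variable is named in the text, and a row in a table would still not reconcile the two definitions.
- **Time point and direction.** Item 4b gives no time point, and the endpoint says change rather than reduction. A reader might call 4b undefined. It is not: the Schedule of Events collects the specific symptom ratings only at baseline and Day 28, the synopsis states that interval for all seven items, and the objectives and Section 2 speak of reduction and improvement.
- **Success rule.** A reader might infer that the plan omits whether 4a and 4b must both be met. The plan states no trial-level success rule. It speaks of multiple primary endpoints and leaves p-value adjustment to the reader, so separate reporting is a fair reading.
- **Group-mean reading.** The 2 points might be meant for the mean. That is possible, but no described test uses them under that reading either.

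**Conclusion.** The concern holds. The synopsis and Section 4 define the primary endpoint differently. Neither settles whether the 2 points apply to each subject or to the group mean, and no described efficacy test uses the threshold or the any-two rule. Following the plan exactly can give p < 0.05 at a mean change of 0.43 to 0.85 points, for an assumed SD of 1.5 to 3.0. The definitional conflict and the gap between endpoint and test rest on the text alone; only the conversion to points depends on the assumed SDs.

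A reader might go further and conclude that the study is underpowered or its tests invalid. Neither follows. The power statement reproduces for change against zero, and at a true mean change of 2 points with SD 3.0 the power against zero is 99.6%. The t-tests are valid for the question they ask. The defect is that this is not the question in the stated endpoint, and it should be corrected before the results are interpreted.

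**What to change.** **Synopsis and Section 4.** Use one definition in both, worded as a reduction from baseline to Day 28. State whether the 2 points apply to each subject or to the group mean. Count overall irritation once.

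**Section 21 and Table 1.** Keep the paired t-tests, and report for each scale:
- the mean reduction with its 95% CI, read against 2 points;
- the proportion of subjects with a reduction of at least 2 points, with an exact 95% CI on the ITT denominator (up to the 55 enrolled). Add the any-two proportion if that rule is kept. Label these proportions descriptive, because a single-arm design has no reference rate.

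State that the t-tests and the 80% power concern change against zero, and that p < 0.05 alone will not be described as meeting the 2-point endpoint.

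**Cost.** Wording in three places and a little more analysis of data already collected; no added subjects or visits. The price is interpretive: a significant t-test alone no longer supports a claim that the primary endpoint was met.
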